## **9.11 EFFICACY ANALYSES**

Efficacy analyses will be performed using the Response Evaluable Set unless specified otherwise. Summary will be provided separately for each Phase 1 part (A, B, E, G) by dose level and for each Phase 2 part (C, D) by tumor type cohort unless specified otherwise. Data will be presented in subject listings.

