7.5. Long-Term Follow-up

Long-term follow-up assessments will be done every 12 weeks (\pm 2 weeks) from the last dose of JTX-2011. All subjects who discontinue study treatment will be followed for:

- Survival: Via telephone or email until a) death, b) withdrawal of consent, c) they are lost to follow-up, d) the Sponsor notifies sites that survival follow-up is no longer required, or e) termination of study by the Sponsor
- Assessment of treatment-related SAEs until resolution to baseline or Grade 0-1.

Subjects discontinuing treatment due to reasons other than documented disease progression will have their tumor assessed (using the same modality that was used during study treatment) every 12 weeks (\pm 2 weeks) for up to 2 years after the last treatment visit, until a) they start a new therapy for their cancer, b) death, c) withdrawal of consent, d) are lost to follow-up, e) the Sponsor notifies sites that tumor assessment is no longer required during long-term follow-up, or f) termination of study by the Sponsor.

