9.4.2. Analysis Set

All Subjects Set will include all subjects who have signed the informed consent and have subject numbers in the electronic clinical database.

The **Safety Population (SAF)** will include all subjects who have been treated with at least one dose of study drug (JTX-2011, nivolumab, ipilimumab, or pembrolizumab). The SAF will be the primary analysis set for all efficacy and safety analyses, unless otherwise specified.

Pharmacokinetic/Pharmacodynamic Analysis Set (PK/PD Set) will include all subjects who received at least one dose of the study drug and who provide at least one observation for at least one of the PK or PD endpoints without protocol violations that would be deemed by the trial pharmacokineticist to interfere with the PK or PD analysis.

Immunogenicity Analysis Set will include all subjects who received at least one dose of the study drug and provided one serum sample that could be successfully analyzed by both a screening and confirmatory validated ADA assay (for ADA analysis) or NAb assay (for NAb analysis).

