#### 6.1.1 SUBSETS OF THE SAF

- Response Evaluable Set: subjects in SAF who have a baseline tumor assessment, and either has at least one post-baseline tumor assessment scan and/or discontinued treatment due to death or disease progression.
- The DLT Evaluable Set: SAF subjects in Phase 1 parts (A, B, E, G) who receive at least one dose of JTX-2011 during the DLT-evaluation period (1st cycle) and complete the DLT-evaluation period (1st cycle) or experience any DLTs.
- Biomarker Analysis Set: SAF who have a baseline sample and at least one post treatment biomarker sample.
- ADA Analysis Set: SAF who have a baseline sample and at least one post treatment ADA sample.

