## 7.12 MISSING DATA

### 7.12.1 IMPUTATION OF NON-DATE MISSING DATA FOR STATISTICAL ANALYSES

Unless otherwise explicitly specified, missing data will not be imputed. All available time to progression or death data will be analysed using appropriate statistical methods that allow for censoring when no progression or death is reported. Subjects with reported shorter treatment and/or follow-up intervals will not be considered to have missing time to progression or death status. Subjects with premature study withdrawal (including lost to follow-up) will be included in any analyses where they contribute data and where they conform to the analysis population of interest.

Subjects without baseline tumor assessments will be considered non-evaluable for ORR and irORR analysis.

When using RECIST v1.1 or irRC criteria to estimate the proportion of responders, all subjects in Response Evaluable Set will be included in the denominator even when their responses are missing.

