### 8.3.2 OBJECTIVE RESPONSE RATE – INVESTIGATOR ASSESSED AND CENTRAL REVIEW

Objective response rate (ORR) is defined as the proportion of subjects with a Best Overall Response (BOR) characterized as either a Complete Response (CR) or Partial Response (PR) as defined by RECISTv1.1 guidelines, relative to the total number of evaluable subjects in the population of interest. Per RECISTv1.1 guidelines, subjects with documented PR or CR will need confirmatory tumor assessments to document tumor response. Subjects without baseline tumor assessments will be considered non-evaluable for this analysis. Responses are only considered if they occur prior to objective progression and the start of subsequent anticancer therapy.

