### 8.3.9 IMMUNE-RELATED OBJECTIVE RESPONSE RATE – CENTRAL REVIEW

Immune-related best overall response (irBOR) will only be evaluated according to central review. The irBOR (as defined by irRC guidelines) is recorded from first dose date until documented disease progression (irPD) or death. The irORR is defined as the proportion of subjects with an irBOR characterized as either a confirmed complete response (irCR) or confirmed partial response (irPR) prior to the initiation of subsequent anticancer treatment or prior to discontinuation of treatment (due to any other reason), whichever is earlier; irORR will be calculated relative to the total number of evaluable subjects. Subjects without baseline tumor assessments will be considered non-evaluable for this analysis.

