### **9.11.1 ANALYSIS OF RECIST v1.1 RESPONSE**

The best overall response (BOR) will be summarized by frequency and percent. The objective response rate (ORR) and disease control rate (DCR) estimates along with the corresponding exact 2-sided 95% CI using the Clopper-Pearson exact method will be provided. This will be done for the both the investigator and the central review response data. Subjects not classifiable under the RECIST 1.1 response categories due to insufficient data or early death will be classified as non-evaluable for BOR, but will be counted in the denominator of response rates (ORR, DCR) calculations.

Waterfall plots for best overall response and maximum percent change from baseline in tumor measurements and spider plots displaying the percent change from baseline in tumor measurements by study day will be displayed for evaluable and subset populations. Additional graphs by disease indication will be created as warranted. All RECIST response assessments will be listed by subject, cohort, phase and visit (including unscheduled). BOR, ORR and DCR will also be included.

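### ORR, irORR and DCR are computed on the Response Evaluable Set with no all-treated rate planned, so these rates can be inflated and never deflated

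*SAP*

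**What the plan says.** Protocol 9.4.2 defines the SAF as everyone given at least one dose of study drug and says: "The SAF will be the primary analysis set for all efficacy and safety analyses, unless otherwise specified".

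SAP 9.11 sets a different default: "Efficacy analyses will be performed using the Response Evaluable Set unless specified otherwise". SAP 6.1.1 defines that set as "subjects in SAF who have a baseline tumor assessment, and either has at least one post-baseline tumor assessment scan and/or discontinued treatment due to death"; stopping treatment because the disease progressed also qualifies. SAP 7.12.1 repeats the denominator for RECIST and irRC responder proportions: "all subjects in Response Evaluable Set will be included in the denominator even when their responses are missing". SAP 8.3.2 adds for ORR: "Subjects without baseline tumor assessments will be considered non-evaluable for this analysis". SAP 8.3.9 has the same exclusion, and there "irORR will be calculated relative to the total number of evaluable subjects".

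SAP 9.11.1 says that subjects who cannot be classified under RECIST "due to insufficient data or early death will be classified as non-evaluable for BOR, but will be counted in the denominator of response rates". SAP 9.11.3 assigns PFS and OS to the SAF. The SAP gives no reason for using a narrower set for the response endpoints and plans no ORR, irORR or DCR on the SAF.

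**The concern.** Response rate and disease control rate are among the Phase 2 primary efficacy measures (SAP 3.1.4). They will be read against the 8% and 20% reference rates in SAP 9.12. SAP 3.3.1 says there is no formal testing, so the reported rate and its exact interval are in effect the result.

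If the denominator omits only subjects who cannot be in the numerator, the error has one direction. A cohort's ORR and its PFS would also be based on different sets of subjects.

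**Working it through.** **Who is dropped.** SAP 6.1.1 requires a baseline assessment, plus either a post-baseline scan or treatment stopped for death or progression. Two groups of treated subjects fall outside:

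1. those without a baseline tumor assessment;
2. those never scanned after baseline whose treatment stopped for another reason, such as toxicity, withdrawal of consent or loss to follow-up.

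Scans after stopping recover part of group 2:

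- Protocol 7.4 asks for a CT at end of treatment unless one was done within 9 weeks. If the screening scan counts, a subject given one dose may not need this CT: 28 days of screening + 28 days to the visit + 7 days of window = 63 days = 9 weeks.
- Protocol 7.5 has 12-weekly scans for subjects who stopped without documented progression, but only "until a) they start a new therapy for their cancer, b) death, c) withdrawal of consent, d) are lost to follow-up" (or the sponsor ends them). Subjects who leave by these routes before any scan remain out.

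**Can a dropped subject be in a numerator?**

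- CR or PR needs a confirmatory assessment (SAP 8.3.2, 8.3.3).
- irCR or irPR needs confirmation at least 4 weeks later (SAP 8.3.8).
- Stable disease at the first scan needs a further scan to count as disease control (SAP 8.3.4).
- A baseline scan outside the 28-day window is made not evaluable by SAP 8.3.1, although SAP 11.3 softens this with the word generally.

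So the answer is no. With r responders, N treated and k dropped, the SAP rate is r/(N − k) and the all-treated rate is r/N. The ratio is N/(N − k), which is at least 1. The two rates are equal only if k = 0 or r = 0.

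**Does SAP 9.11.1 bring them back?** Read alone, it could. It sits under 9.11, whose default is the Response Evaluable Set, and 7.12.1 names that set as the denominator. For subjects without a baseline assessment, 8.3.2 says they are non-evaluable. The natural reading is that 9.11.1 protects unclassifiable subjects inside the set.

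**The plan's own figure.** SAP 9.12: null ORR 0.08, alternative 0.20, 90% power, two-sided 5%.

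n = [(1.960·√(0.08·0.92) + 1.282·√(0.20·0.80)) / 0.12]² = 75.7, so 76. This matches. With success at more than 10 of 76, the exact upper tail is 3.9% at 0.08 and 91.6% at 0.20 (no futility stop). The figures below therefore use 76 and 11 responders.

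**Size.** The documents give no rate of never-scanned subjects, so every k is an assumption. Exact limits are Clopper-Pearson, as in SAP 9.11.1: lower = Beta(0.025; r, n − r + 1), upper = Beta(0.975; r + 1, n − r).

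15 treated:

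| k | 3 responders (95% CI) | 2 responders | 8 with disease control |
|---|---|---|---|
| 0 | 20.0% (4.3–48.1) | 13.3% | 53.3% |
| 1 | 21.4% (4.7–50.8) | 14.3% | 57.1% |
| 2 | 23.1% (5.0–53.8) | 15.4% | 61.5% |
| 3 | 25.0% (5.5–57.2) | 16.7% | 66.7% |

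76 treated, 11 responders:

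| k | ORR | 95% CI |
|---|---|---|
| 0 | 14.5% | 7.5–24.4 |
| 4 | 15.3% | 7.9–25.7 |
| 6 | 15.7% | 8.1–26.4 |
| 8 | 16.2% | 8.4–27.1 |

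Dropping 6 of 76 (7.9%) takes the lower limit from below to above 8% with no change in responders.

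**The case against.** **No breach.** The protocol allows another set where specified, and the SAP specifies one. That stands. The complaint is an unexplained choice with a predictable direction.

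**Few are dropped.** Phase 2 eligibility requires a measurable lesion and imaging is a screening procedure, so the no-baseline group should be close to empty in Parts C and D. Never-scanned subjects who stopped for death or progression stay in the denominator, and so do missing responses inside the set. This limits the size but does not change the direction.

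**SAP 9.11.1 may already cover them.** Its wording on insufficient data is broad, 9.11 yields where another rule is specified, and the no-baseline exclusion names ORR and irORR but not DCR. The narrower reading is more natural, but there is a real ambiguity. On the broad reading, 7.12.1 and 8.3.2 conflict with 9.11.1, so an edit is needed either way.

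**The 76-subject example is selected.** This is correct. With 12 of 76 the all-treated lower limit is already 8.4%, and with 10 responders and 8 dropped it is still 7.3%. No plan rule compares a confidence limit with 8%. Table 9 counts responses, so with 15 or 76 treated subjects its decisions do not change. SAP section 5 puts expansion at about 49, not 76. The example shows what can happen and is not a forecast.

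**PFS barely differs.** SAP 8.3.5.2 censors most never-reassessed subjects at first dose, so they add little to SAF-based PFS. That weakens the argument about different subjects. It does not apply to OS.

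**A reader could compute the SAF rate.** SAP 9.1 tabulates the analysis populations, so responders over SAF can be worked out. That does not replace a planned estimate with its interval.

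**Conclusion.** The concern holds. As written, the ORR, irORR and DCR denominators leave out treated subjects who can only be failures, so each rate equals or exceeds the all-treated rate. The inflation factor is N/(N − k): 7%, 15% or 25% in relative terms for 1, 2 or 3 dropped from 15, and zero if nobody is dropped.

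In a 15-subject cohort the shift is small against the interval width. In an expanded cohort it can move a borderline interval across the plan's 8% reference. The conclusion on direction rests on the response definitions and on reading SAP 9.11.1 together with 7.12.1 and 8.3.2. The size rests entirely on assumed numbers dropped. This should be changed, because the correction is cheap and restores the protocol's default, but it does not threaten the study's decision rules.

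**What to change.** - In SAP 9.11, 7.12.1, 8.3.2 and 8.3.9, make the SAF the primary denominator for ORR, irORR and DCR in Parts C and D.
- Count treated subjects without a baseline or post-baseline assessment as non-responders and as not having disease control.
- State in SAP 9.11.1 that the denominator is all treated subjects, which removes the ambiguity there.
- Use the same denominator for the Part A and Part B columns of the SAP 9.11.5 subgroup tables, so that one table does not mix sets.
- Keep the Response Evaluable Set as a sensitivity analysis, and report per cohort how many SAF subjects it drops and why.

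The cost is SAP wording and one denominator flag. No new data are needed. Reported rates become slightly less favourable.

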### **9.11.1 ANALYSIS OF RECIST v1.1 RESPONSE**

The best overall response (BOR) will be summarized by frequency and percent. The objective response rate (ORR) and disease control rate (DCR) estimates along with the corresponding exact 2-sided 95% CI using the Clopper-Pearson exact method will be provided. This will be done for the both the investigator and the central review response data. Subjects not classifiable under the RECIST 1.1 response categories due to insufficient data or early death will be classified as non-evaluable for BOR, but will be counted in the denominator of response rates (ORR, DCR) calculations.

Waterfall plots for best overall response and maximum percent change from baseline in tumor measurements and spider plots displaying the percent change from baseline in tumor measurements by study day will be displayed for evaluable and subset populations. Additional graphs by disease indication will be created as warranted. All RECIST response assessments will be listed by subject, cohort, phase and visit (including unscheduled). BOR, ORR and DCR will also be included.

### **9.11.2 ANALYSIS OF IRRC RESPONSE**

- The irBOR and irORR will be summarized as above in 9.11.1 by frequency and percent along with the corresponding exact 2-sided 95% CI using the Clopper-Pearson exact method however this analysis will only include the central review response data.

Waterfall plots for best overall response and maximum percent change from baseline in tumor measurements and spider plots displaying the percent change from baseline in tumor measurements by study day will be displayed for evaluable and subset populations. Additional graphs by disease indication will be created as warranted. All irRC response assessments will be listed by subject, cohort, phase and visit (including unscheduled). The irBOR and irORR will be included.

#### **9.11.3 ANALYSIS OF TIME-TO-EVENT ENDPOINTS**

Estimates of the duration of response (DOR), landmark and overall survival (OS) and landmark and progression free survival (PFS) will be described using the Kaplan-Meier estimates. If there are sufficient number of events, the median, first and third quartiles (time) and corresponding 2-sided 95% confidence interval based on the Brookmeyer-Crowley methods will be presented. Kaplan-Meier methods will be used to estimate the probability and figures will use the KM estimates to identify the number of subjects at risk at each scheduled visit and will display censored times graphically on the curve. Probability of event estimates will be summarized in a table for various intervals e.g., 3, 6, 9 and 12 months. DOR and PFS will be analysed based on both investigator response data and central review response data. If supported by the data, analyses by disease cohort across phases 1 and 2 may be produced. Analyses of PFS and OS will be done using the SAF and analyses of DOR will be done only for responders (with confirmed CR or PR). KM figures will be produced for PFS and for some selected OS by cohort in both the phase I and phase II.

#### **9.11.4 COMPARISON OF INVESTIGATOR VERSUS CENTRAL REVIEW RESPONSE DATA**

Summaries comparing the BOR and PFS as determined by the investigator versus the central review using RECISTv1.1 criteria will be presented.

#### **9.11.5 SUBGROUP ANALYSES**

Analysis of response and time to event endpoints outlined above in sections 9.11.1 to 9.11.3 may be performed for the following subgroups:

- ICOS IHC high vs ICOS IHC low on archival tumor sample
- ICOS IHC high vs ICOS IHC low on fresh biopsy
- ICOS IHC 0 vs ICOS IHC 1,2,3 on archival tumor samples
- ICOS IHC 0 vs ICOS IHC 1,2,3 on fresh biopsy
- Prior IO therapy yes or no
- Prior PD-1/PD-L1 therapy yes or no

Subgroup analysis tables will be provided separately for JTX-1011 monotherapy (including 0.1 mg/kg, 0.3 mg/kg and total columns for Part A and tumor cohorts, total columns for Part C) and JTX-1011+Nivolumab combination therapy (including 0.1 mg/kg+ Nivolumab, 0.3 mg/kg + Nivolumab and total columns for Part B and tumor cohorts, total columns for Part D). Additional subgroup analysis, if conducted, will be documented in a separate exploratory analysis plan.

#### **9.11.6 ICOS TARGET ENGAGEMENT ON CD4 T CELLS**

ICOS target engagement on CD4 T cells will be presented as % target engagement for each subject in listings. TE will also be presented in tabular format by dose level for each Phase 1 part (A, B, E, G) and by tumor type cohort for each Phase 2 part (C, D) using Biomarker Analysis Set for the following:

- Number and percentage of subjects at each available time point with TE  $\geq$  70%
- Number and percentage of subjects with  $\geq$  70% TE at every measured time point after first dose through C2D1
- Number and percentage of subjects with TE  $\geq$  70% after first dose and descriptive summary of duration of TE  $\geq$  70% after first dose, which is defined as the number of days with TE  $\geq$  70% (only for subjects ever having TE  $\geq$  70% post dose)
- Number and percentage of subjects with TE  $<$  30% after first dose and descriptive summary of duration of TE  $<$  30% after first dose, which is defined as the number of days with TE  $<$  30% (only for subjects ever having TE  $<$  30% post dose)
- Number and percentage of subjects at each available timepoint with TE  $<$  30%
- Number and percentage of subjects at each available time point with TE = 0

The relationship of PK endpoints and ICOS target engagement may also be explored separately using pharmacokinetic/pharmacodynamic (PK/PD) modelling techniques. Any PK/PD modelling will be conducted under a separate analysis plan and reported separately.

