6.2.1. Initiation of Parts C, D, F, and H

Part C

Assuming that there are no safety concerns in Part A, enrollment in Part C will begin once a dose is identified from Part A that results in approximately 70% sustained ICOS TE through day 21 and PK that support dosing q3w or q6w or the MTD is identified. This is anticipated to be one dose level above the dose level selected for Safety/PK/PD Expansion cohort AP1.

Part D

Assuming that there are no safety concerns in Part B, enrollment in Part D will begin once a dose is identified from Part B that results in approximately 70% sustained ICOS TE and PK that support dosing q3w or the MTD is identified. This is anticipated to be one dose level above the dose level selected for Safety/PK/PD Expansion cohort BP1.

Part F

Enrollment in Part F will begin assuming that there are no safety concerns and the RP2D has been determined from Part E.

Part H

Enrollment in Part H will begin assuming that there are no safety concerns and the RP2D has been confirmed from Part G.

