In tabulation of PK or PD data, scheduled samples that could not be obtained or analyzed, or samples from which concentration data was identified by the bioanalytical lab as below the limit of quantitation (BLQ) will be ignored and not replaced by zero at any time point except the pre-first dose baseline for PK. Descriptive statistics of concentrations or biomarkers at specific time points will be calculated only when at least $\frac{1}{2}$ of the individuals have concentrations or biomarker data within validated ranges. The overall sample size to decide whether the " $\frac{1}{2}$ rule" is fulfilled will be based on the total number of samples intended to be drawn for that time point.

Dose proportionality of the pharmacokinetic endpoints AUC_{0-tz} , $AUC_{0-\infty}$, and t_{ma} will be explored based on a standard regression model. Based on the estimate for the slope parameter β , a two-sided-95% confidence interval for the slope will be computed. The assumption of a linear relationship between the log-transformed pharmacokinetic endpoint and the log-transformed dose will be checked. Perfect dose proportionality would correspond to a slope of 1.

If dose proportionality over the entire dose range investigated cannot be shown, an attempt will be made to identify dose range(s) where dose proportionality can be assumed.

Attainment of steady state will be explored by pairwise comparison of the trough concentrations of JTX-2011 measured at the beginning of each treatment cycle. If trough concentrations cannot be reported because they are BLQ, attainment of steady state will be assessed from a population PK model.

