### **3.2.4 PHARMACODYNAMIC ENDPOINTS**

#### **3.2.4.1 ICOS TARGET ENGAGEMENT ON CD4 T CELLS**

ICOS target engagement on CD4 T cells is the primary pharmacodynamic biomarker in this study. Determination of the RP2D of JTX-2011 as monotherapy (Part A) or as part of a combination therapy (Part B, E or G) was a primary objective in Phase 1 parts (A, B, E, G) and confirmation of the RP2D of JTX-2011 as monotherapy (Part C) or as part of a combination therapy (Part D) was a primary objective in Phase 2 Parts (C, D). Evaluation of ICOS target engagement was the marker of pharmacodynamic activity on which selection and confirmation of the RP2D was based in this study.

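### The SAP row for at least 70% target engagement through C2D1 does not require a C2D1 sample, so missing late samples can only leave the percentage unchanged or raise it

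*SAP*

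**What the plan says.** SAP 9.11.6 lists, among its TE tables, the number and percentage of subjects with at least 70% "TE at every measured time point after first dose through C2D1". Tables are by dose level within Parts A, B, E and G and by tumor cohort within Parts C and D. They use the Biomarker Analysis Set, which SAP 6.1.1 defines as "SAF who have a baseline sample and at least one post treatment biomarker sample".

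Neither section asks for a C2D1 value or a minimum number of TE samples. SAP 7.12.1 adds: "Unless otherwise explicitly specified, missing data will not be imputed", and nothing is specified for TE. Protocol 9.5.3 says that, when PK or PD data are tabulated, "scheduled samples that could not be obtained or analyzed" are ignored. Its rule that half the samples must be available covers descriptive statistics at a given time point, not this subject-level count.

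The nearest protocol counterpart is the condition for opening Part C, a Part A dose giving "approximately 70% sustained ICOS TE through day 21" (Protocol 6.2.1). SAP 3.2.4.1 calls TE "the marker of pharmacodynamic activity on which selection and confirmation of the RP2D was based in this study".

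**The concern.** The row reads as a statement about the whole interval up to C2D1, but the rule tests only the samples that exist. Someone who leaves or misses the visit after one high early value is counted with those who were measured at C2D1 and were still high. The late sample is the one most likely to show a fall in TE, so losing it removes a chance to fail. This is a rule with a known direction of error, and more than a missing detail.

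At stake is the reading of the SAP's closest summary of maintained TE, for a marker that the SAP ties to dose selection and confirmation. A second, smaller matter is that C2D1 falls on different days under the two schedules, so one row label covers two time spans when parts are compared.

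**Working it through.** **Day of C2D1.** With the first dose as Study Day 1 (SAP 7.4), C2D1 is cycle length plus 1. On q3w that is 21 + 1 = Day 22, which reproduces the 22 days in Protocol 1.4.2.2. In Part E, where JTX-2011 is given q6w (Protocol 5.3), it is 42 + 1 = Day 43. Part E also has a C1D22 visit with TE sampling (Protocol 7.2.6).

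**Which samples stand before C2D1.** TE is taken in all parts on C1D1 and C1D2 (Protocol 7.2.1, 7.2.2). Day 8 and Day 15 sampling is limited to Parts A, B, E and G (Protocol 7.2.4, 7.2.5). In the q3w cohorts of Parts C and D, a subject without C2D1 has only data from about the first 24 hours.

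**Direction.** The criterion is that all measured values are at least 70%. Take a subject with at least one other post-dose TE value and delete the last one. If it was below 70% and the rest were high, a failure becomes a success; otherwise nothing changes. The denominator stays the same.

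**Size.** The documents give no TE rates and no missingness, so every input here is an assumption. Let s be the share truly at or above 70% through C2D1, m the share with no C2D1 sample, and e the share of those who were high at their early samples.

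- Row as written: s(1 - m) + e·m
- Excess over s: m(e - s), which is m(1 - s) when e = 1

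Excess in percentage points with e = 1:

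| s | m = 10% | m = 20% | m = 30% |
|---|---|---|---|
| 90% | 1 | 2 | 3 |
| 70% | 3 | 6 | 9 |
| 50% | 5 | 10 | 15 |
| 30% | 7 | 14 | 21 |

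For example, s = 50% and m = 20% gives 0.50 × 0.80 + 0.20 = 0.60. With e = 90% instead, it gives 0.40 + 0.18 = 0.58. This is an upper-end approximation: subjects who were high early are probably likelier than average to have stayed high, which narrows the gap.

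**In counts (assumed cohort of 15).** Twelve have a C2D1 sample, of whom six meet the criterion; three have only early high values.

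- Row as written: (6 + 3)/15 = 60%
- C2D1 value required, three shown as not assessed: 6/12 = 50%
- Three treated as not meeting the criterion: 6/15 = 40%

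**Choice of denominator.** Excluding everyone without a C2D1 value would create a new upward bias. Take ten subjects: five pass, three fail at C2D1, and two were already below 70% on Day 8 with no later sample. The row as written gives 5/10 = 50%. Excluding the last two gives 5/8 = 62.5%. Keeping them as known failures restores 5/10.

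**The case against.** The strongest reply is that nothing depends on this row. The RP2D for Parts A and B was already set in protocol version 9.0 (Protocol 6.1.1), before the SAP of March 2020. Protocol 6.6 bases the RP2D on discussion of safety, PK, pharmacodynamics and infusion tolerability. The SAP has no hypothesis tests (3.3.1) and no comparisons (7.10). All of this stands. A reader might infer from SAP 3.2.4.1 that the row determined the RP2D, but that section names the marker and no section makes this tabulation a decision rule. A reader might also infer that one missing sample could tip the two-in-three rule for opening the expansion cohorts. That rule concerns TE on Day 8 or on Day 21 (Protocol 6.5), a single-time-point criterion, and those cohorts had already enrolled.

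Second, the effect may be small. Protocol 1.4.2.2 reports, from a small data set, that peripheral TE was saturated through C2D1. If that holds in Parts C and D, which dose at the RP2D, the top line of the table is the relevant one. This limits the size but leaves the direction unchanged.

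Third, the section also gives TE of at least 70% at each time point, its duration, and subject listings, so C2D1 can be seen separately. In addition, dose-escalation subjects who leave before completing C2D1 assessments without a DLT are replaced (Protocol 6.8.2). Both help, but neither corrects the subject-level count. A replaced subject can remain in the Biomarker Analysis Set, and the replacement rule does not reach Parts C and D.

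Fourth, through C2D1 can be read as through the next JTX-2011 dose, which is coherent for each schedule. Tables are by part, so Part E is not pooled with the q3w parts, and the day-21 condition belongs to the opening of Part C. A reader might infer that Part E is held to a protocol criterion at twice the duration; the documents do not say so. What remains is labelling and comparability.

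**Conclusion.** The point holds as a biased counting rule in a descriptive table. As written, the row is an upper bound on the share with TE of at least 70% through C2D1 among subjects with at least one post-dose TE value. Missing late samples leave it unchanged or raise it, most readily in Parts C and D. The plausible excess runs from about 1 point (s = 90%, m = 10%) to about 10 points (s = 50%, m = 20%), and more only if both missingness and loss of engagement are substantial. These figures assume that everyone without a C2D1 sample was high early and would have stayed high at the average rate. No error rate, sample size or documented dose decision changes. The difference between Day 22 and Day 43 is a labelling matter.

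**What to change.** In SAP 9.11.6:

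1. Count a subject as at or above 70% through C2D1 only if the C2D1 TE value is non-missing and every measured post-dose value through C2D1 is at least 70%.
2. Keep any subject with a measured value below 70% in the denominator as not meeting the criterion, whether or not C2D1 was sampled.
3. Report subjects with no value below 70% and no C2D1 sample in a separate row, C2D1 not assessed, outside the denominator. This also places subjects who enter the set on another biomarker sample and have no post-dose TE at all, whom the present wording leaves undefined.
4. Add a sensitivity count that treats the not-assessed subjects as not meeting the criterion. With the present count it brackets the answer, 40% to 60% in the example of 15.
5. Label the window in days: Day 22 on q3w, Day 43 in Part E. For Part E, add a row through Day 22 from the C1D22 sample already scheduled, for comparison with the q3w parts.

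The cost is a change of wording and one or two extra table rows, with no new data. The denominator shrinks by the number not assessed, which should be slight if few C2D1 samples are missing, and the new row shows the number.
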